#### A1. Main Title

COMPARATIVE EFFECTIVENESS OF TWO ACELLULAR MATRICES PRODUCTS (DERMACELL V. INTEGRA) FOR MANAGEMENT OF DEEP DIABETIC FOOT ULCERS - A RANDOMIZED CLINICAL TRIAL

## A3a. Financial Conflict of Interest

Does any member of study personnel (Investigator (including investigator's spouse and/or dependent children)) that are involved in the design, conduct, or reporting of the research have a Significant Financial Interest (SFI) that would reasonably appear to be affected by the research for which funding is sought and/or associated with an entity/business that would reasonably appear to be affected by the research?

No

## A5. Funding Source:

Organization: LIFENET HEALTH

#### A6b. Research conducted outside of the United States:

Country:

Facility/Institution: Contact/Investigator: Phone Number:

If documentation of assurances has not been sent to the Office of Research, please explain:

## A7. Research Category:

#### A8. Therapeutic Intent

Does this trial have therapeutic intent?
No

## A9. ClinicalTrails.gov Registration

Does this trial meet the definition of an Applicable Clinical Trial and require registration on ClinicalTrials.gov?

No, this clinical trial does not meet the definition of an Applicable Clinical Trial. Registration is not required.

# Section B: Exempt Request

# **B. Exempt From IRB Review**

Not Applicable

# Section C: Background Information

Diabetes-related foot ulcers (DFUs) are a leading cause of hospitalization and amputation worldwide, and account for 33% of all direct costs of diabetes care in the US. Ulcers requiring acute care can result in treatment costs of up to US\$70,000 per event, varying with the severity of the wound. Once the skin is ulcerated, it is susceptible to becoming infected and ultimately amputation in particular in case of deep DFUs. To manage the cost and avoid hospitalization and amputation, wound should be immediately closed. But this is often challenging in diabetic foot with deep ulcers. Wound healing is a dynamic process involving interactions between cells, extracellular matrix (ECM) and growth factors that reconstitutes tissue following injury. ECM plays an important role in tissue regeneration and is the major component of the dermal skin layer. Recognition of the importance of the ECM in wound healing has led to the development of wound products that aim to stimulate or replace the ECM in particular in case of deep tissue destruction because of deep DFUs. It is known from the literature that chronic or hard-to-heal wounds are characterized by a disrupted or damaged ECM that cannot support wound healing. Thus treatment strategies based on use of biologic scaffold materials for management of chronic and deep wounds has increased dramatically during the past two decades. These scaffolds include those comprising an intact extracellular matrix (ECM) or individual components of the ECM, and those comprising hybrids incorporating a synthetic component with a biologic component. DermACELL (LifeNet Health, Virginia Beach, VA) is acellular dermal matrices (ADM), which has been shown to be effective in treating chronic DFUs in a clinical trial.

Another ADM product available in the market is made by Integra® (Bilayer Matrix Wound Dressing, Integra LifeSciences). However, advantages/disadvantages of one compared to the other are unclear. Figure 2 (Please see protocol in section S)illustrates the case showed in the figure 1 treated by both Integra and DermaCell (One of the wound was treated by Integra and the rest were treated by DermaCell). As it can be seen the thickness of Integra is higher than DermalCELL,

\*\*\*Please note that this is a reliance protocol\*\*\*

which may make it relatively more difficult to apply with potential further complications including likelihood of infection, poor tissue mechanics outcomes (e.g. presence of scarring or tissue biomechanics properties leading to increase in shear or pressure post healing thus increasing likelihood of recurrence of the ulcer), and patient centered outcomes like smell, pain, and comfort.

# Section D: Purpose and Objectives

\*\*\*Please note that this is a reliance protocol\*\*\*

The primary objective of this prospective, randomized trial is to compare the outcomes of DermaCELL with Integra. We assumed that the wounds outcomes (e.g. weekly wound size change, time to heal, time to successful wound granulation) are comparable between DermaCELL and Integra. However, from operation and patient centered outcomes, there may be some noticeable differences. For instance, DermaCELL, thanks to its mesh structure, thin thickness, and no need for hydration, may be easier to apply with shorter time than Integra. The factors are of key importance in operation room (OR) setting and could reduce overall cost of application and needs in using OR resources. Other important outcomes least addressed in prior studies are number of grafts failing, adverse events (e.g. amputation, infection, etc), cost of wound healing treatment, tissue biomechanics, which may lead to recurrence of ulcers (e.g. formation of tissue scarring), and other patient-centered outcomes (e.g. pain, quality of sleeping, wound smelling, etc). For instance, many patients are unhappy with smelling of wounds, which make them embarrassed among their family members like grand kids. Thus reducing wound smelling during activities of daily living is often considered as an important patient centered outcomes.

# Section E: Protocol Risks/Subjects

# E1. Risk Category

Category 1: Research not involving greater than minimum risk.

## E2. Subjects

Gender:

**Both** 

Age:

Adult (18-64 yrs), Geriatric (65+ yrs)

Ethnicity:

All Ethnicities

Primary Language:

English, Spanish

Groups to be recruited will include:

**Patients** 

Which if any of the following vulnerable populations will be recruited as subjects?

Vulnerable populations require special protections. How will you obtain informed consent, protect subject confidentiality, and prevent undue coercion?

#### E3. Pregnant woman/fetus

Will pregnant women and/or fetuses (as described in 45 CFR 46 Subpart B) be enrolled in the research? No

#### E4. Neonates

Will neonates of uncertain viability or nonviable neonates (as described in 45 CFR 46 Subpart B) be enrolled in the research? No

#### E5. Children

Will children be enrolled in the research?

No

# Section F: Design/Procedure

## F1. Design

Select one category that most adequately describes your research:

c) Pilot

Discuss the research design including but not limited to such issues as: probability of group assignment, potential for subject to be randomized to placebo group, use of control subjects, etc.

Thirty four (n=50) patients with diabetes (age 18 years or older) with non-infected deep wounds (grades 2 in the Wagner Ulcer classification) will be randomized into two groups, 17 subjects per group each. The group one will be treated by Meshed DermaCELL and group two will be treated by Meshed Integra template.

The primary outcomes are time to granulation, successful granulation at 8 weeks, and number of failures (e.g. amputation, infection, rejection, re-application) within 8 weeks. Secondary outcomes include time to apply, weekly speed of wound healing after successful granulation and transition to standard wound therapy, success of wound healing at 12 weeks and @16 weeks, cost of wound treatment upto 16weeks (based on patient electronic record), tissue biomechanics after wound healing (e.g. presence of scarring or tissue biomechanics properties leading to increase in shear or pressure post healing), change in skin perfusion (assessed with SPP), change in thermography response, recurrence of ulcers up to 6 months post healing, and other patient centered outcomes including perception of pain, physiological stress response as surrogate of pain (e.g. heart rate variability during dressing change), sleep quality (assessed by PSQI and sensor-based sleep quality index), wound smelling (assessed by Likert scale), and patient perception of benefit (assessed by technology acceptance model, TAM based on perception of benefit and attribute of benefits).

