Device Acceptability Questionnaire: The subject will be handed a questionnaire to evaluate the study device and provide feedback to the research team. We will be asking about level of satisfaction with the product. These may be questions about the time spent to apply the product, the level of comfort, appearance of the product, the appearance of the healed wound (e.g. presence of scarring), ease of walking or standing with the product and after healing, etc.

Matrix Application: During the subject's wound treatment (either in OR or outpatient clinic), the physician will apply the dermal matrix from the group they were placed. The researchers will write down the duration needed for full application of the product. For accurate estimation of time needed for preparation and application, the whole process may be video-recorded for offline estimate of each time.

Vascular Assessment: We will assess perfusion of the macro-circulation with arterial Doppler studies and micro-circulation with Skin Perfusion Pressure measurements. Ankle Brachial Index (ABI) will be measured on both extremities. We will also use the SensiLase system (Väsamed) to measure Skin Perfusion Pressure (SPP) in mmHg. Additionally, we may use the LUNA or SPY Device for Indocyanine Green Fluorescence Imaging. For this purpose a fluorescent agent may be injected into the subject's body to allow us observe the blood circulation to the wound. Indocyanine Green Fluorescence Imaging (SPY or Luna) may be performed based on the medical judgment of the physician. Highly qualified medical/clinical staff will perform this measurement. If so, measurement will take place only during baseline and treatment day.

Wound Photo: At every visit, the Medical/Researcher using a standard digital camera will take a digital photo of the wound. We will ask the subject's permission to take photos/video.

Wound Assessment: Evaluations will be based on data collected from wound assessments and photographs. We use acetate tracings and digital photos. Additionally, we will use thermal imaging to track inflammation.

Thermal Image: A thermal camera will be used to obtain an image of the wound and observe swelling.

Wifi Wound Classification: Podiatrist or vascular surgeon will evaluate the health and wellness of the subject's feet in compliance of standard of care

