The description of every visit is below. Screening/Baseline Visit \*duration of visit 90 minutes This visit will take place at Baylor St. Lukes Medical Center during your surgery day. The researchers will perform as described above: Medical History, Questionnaires (Pain, Social Factors, and Quality of Life, Sleep Quality, Cognitive Assessment, Frailty), Matrix application, Upper Extremity Test, Peripheral Neuropathy, Thermal Image, Vascular Assessment, Wound Assessment, Wifi Wound Classification, and Wound photo.

Visit 1, One Week Later \*duration 50 minutes This visit will take place at Baylor Clinic for a regular follow up appointment. The researchers will perform as described above: Pain Questionnaire, Adverse Event Reporting, Dressing Change, Wound Photo, and Wound Care.

Visit 2, Two Weeks Later \*duration 70 min This visit will take place at Baylor Clinic for a regular follow up appointment. The researchers will perform as described above: Adverse Event Reporting, Wound Assessment, Thermal Image, Dressing Change, Wound Photo, and Wound Care.

Visit 3, Three Weeks Later \*duration 50 min This visit will take place at Baylor Clinic for a regular follow up appointment. The researchers will perform as described above: Adverse Event Reporting, Dressing Change, Wound Photo, and Wound Care.

Visit 4, Four Weeks Later \*duration 70 min This visit will take place at Baylor Clinic for a regular follow up appointment.

The researchers will perform as described above: Pain Questionnaire, Adverse Event Reporting, Sleep Quality Questionnaire, Wound Assessment, Dressing Change, Wound Photo, Thermal Image, and Wound Care.

Visit 5, Five Weeks Later \*duration 70 min This visit will take place at Baylor Clinic for a regular follow up appointment. The researchers will perform as described above: Adverse Event Reporting, Dressing Change, Wound Photo, Granulation Assessment, and Wound Care.

Visit 6, Six Weeks Later \*duration 70 min This visit will take place at Baylor Clinic for a regular follow up appointment. The researchers will perform as described above: Adverse Event Reporting, Dressing Change, Thermal Image, Wound Photo, Granulation Assessment, and Wound Care.

Visit 7, Seven Weeks Later \*duration 70 min This visit will take place at Baylor Clinic for a regular follow up appointment. The researchers will perform as described above: Adverse Event Reporting, Dressing Change, Wound Photo, Granulation Assessment, and Wound Care.

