# Section G: Sample Size/Data Analysis

#### G1. Sample Size

How many subjects (or specimens, or charts) will be used in this study? Local: 50 Worldwide: 50

Please indicate why you chose the sample size proposed:

There is no prior studies to report the major primary outcomes for comparison between DermaCELL and Integra. Based on interviewing our podiatrist who worked with both Integra and DermaCELL, we estimated the time needed to apply each matrices in the OR. We hypothesized that time needed to apply DermallCELL is approximately 3±2 min while the time needed to apply Integra is estimated to be 5±2min (Cohen¿s effect size d=1). Assuming an alpha of 5% and power of 80% and two tailed t-test comparison, 17 subjects per group needed to be recruited to observe a significant difference between two groups from point of view of application time. We anticipate that this sample size should be also sufficient to observe noticeable trend in other outcomes. Based on results of this study, another RCT may be addressed to clinically validate the

observed noticeable trends. Alternatively, the sample size may be increased upon available of budget, approval of sponsor, and noticeable observed trend based on the first 20 recruited subjects (ten per group).

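### F1 gives both 34 and 50 as the sample size, and G1 gives 50 but justifies only 17 per group; one total with a matching group size is needed

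*Combined protocol and SAP*

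**What the plan says.** Section F1 (Design) describes the population as "Thirty four (n=50) patients with diabetes (age 18 years or older) with non-infected deep wounds". The words say 34 and the figure in brackets says 50. The same sentence continues that these patients "will be randomized into two groups, 17 subjects per group each", so the group sizes add up to 34.

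Section G1 (Sample Size) answers the form question "How many subjects (or specimens, or charts) will be used in this study" with "Local: 50 Worldwide: 50". The justification beneath it assumes application times of 3±2 min for DermACELL and 5±2 min for Integra (d = 1), a two-tailed t test, alpha 5% and power 80%, and concludes that "17 subjects per group needed to be recruited to observe a significant difference between two groups from point of view of application time". G1 then adds that "the sample size may be increased upon available of budget, approval of sponsor, and noticeable observed trend based on the first 20 recruited subjects", which means 10 in each arm. It gives no target or maximum for that increase.

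F1 lists time to apply among the secondary outcomes. The primary outcomes in F1 and G2 are time to granulation, successful granulation at 8 weeks, and number of failures within 8 weeks.

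**The concern.** Two entries say 50 (F1's bracket and G1's count). Three say or imply 34 (F1's words, F1's group size and G1's calculation). They cannot all describe the same trial. F1 attaches both totals to the patients who are randomized, so the conflict is not simply one between patients screened and patients randomized.

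The planned total tells the investigator, the ethics board and a later reader when recruitment is complete. As printed, that could be at 34 or at 50. The optional increase adds to the doubt: a reader cannot tell whether 50 is the starting plan, the result of the increase, or a number that the increase could still exceed.

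**Working it through.** **Inputs, all from G1.** Means 3 and 5 min, so the difference is 2 min; SD 2 min in each arm; d = 2/2 = 1; two-sided alpha 0.05; two-sample t test; power 80%; equal groups.

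**Formula.** With n per group, the degrees of freedom are 2n − 2 and the noncentrality is d·√(n/2). Power is the probability that a noncentral t variable with these parameters falls outside ± the 97.5% point of the central t.

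**The plan's own figure.** Solving for 80% power gives n = 16.71, rounded up to 17 per group. Around that value and at the larger total:

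| n per group | Total | df | Critical t | Noncentrality | Power |
|---|---|---|---|---|---|
| 16 | 32 | 30 | 2.042 | √8 = 2.828 | 78.1% |
| 17 | 34 | 32 | 2.037 | √8.5 = 2.915 | 80.7% |
| 25 | 50 | 48 | 2.011 | √12.5 = 3.536 | 93.4% |

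The normal approximation, 2(1.960 + 0.842)²/d² = 15.7, gives 16 per group. The plan's 17 is the t-test answer and reproduces exactly.

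**Totals.** 2 × 17 = 34, not 50. The gap is 50 − 34 = 16 patients, or 8 per group, which is 16/34 = 47% of the smaller total.

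**What each total can detect at 80% power.** At 17 per group, d = 0.99, or 0.99 × 2 = 1.98 min. At 25 per group, d = 0.81, or 0.81 × 2 = 1.62 min.

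So F1's group size and G1's calculation agree with each other and with a total of 34. Nothing in F1 or G1 produces 50.

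**The case against.** The strongest reply is that G1 states a minimum. Seventeen per group are needed for application time, and enrolling 50 meets that need with room to spare. This stands. A reader might infer that G1's 17 per group and 80% power become wrong if 50 is the plan. They do not; they simply fail to explain the extra 16 patients. The entries that cannot stand beside n = 50 are F1's words for the total and its group size.

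A second reply is that 50 may be the increased size that G1 allows, entered after budget and sponsor approval, with the other entries left unchanged. That is plausible and would explain the mixed phrase in F1. But G1 only says that the size may be increased, names no target, and does not report that an increase took place. If it did, F1 was only partly updated.

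A third is that 50 may rest on attrition, higher power, or a combination. A reader might go further and infer that no usual basis leads to 50. The documents do not support that: they are silent, and section S, to which Sections C and L refer for further material, is not in the available text. The accurate statement is that no basis is given here. A basis found in section S would still leave the conflict within F1.

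Finally, F1 labels the study a pilot, and application time is adequately powered at either total. Both are true and limit the consequence, but a pilot still needs one number.

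**Conclusion.** The point holds as an internal contradiction in the planned sample size: 34 against 50, or 17 against 25 per group. The calculation for 17 per group is correct. On G1's assumptions (2-min difference, SD 2, two-sided 5%), power is 80.7% at 34 patients and 93.4% at 50. These figures assume that every randomized patient contributes an application time.

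Two stronger readings should be set aside. A reader might infer that the trial is underpowered; for application time it is not, at either total. For the primary outcomes the plan makes no power calculation, so the discrepancy shows nothing about them in either direction. A reader might also infer something about type I error from the optional increase after 20 subjects. G1 gives no outcome, threshold, direction or maximum for it, so the documents do not support a claim that the error rate is, or is not, affected.

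This should be fixed, but it is a correction of the text and does not call the design into question.

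**What to change.** State one total, with the matching group size and power, in both F1 and G1. Either:

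- 34 patients, 17 per group, about 81% power, correcting both entries of 50; or
- 50 patients, 25 per group, about 93% power, correcting F1's words and group size and adding the basis for 50 to G1.

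In either case, say that the power refers to a 2-min difference (SD 2) in application time, which is a secondary outcome, and that no power is claimed for the three primary outcomes. Say also whether 50 already includes the optional increase and whether it is the maximum.

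The cost is a few lines of wording. If 50 is already the plan, no patients are added. If 34 is chosen, 16 fewer are enrolled and power for the 2-min difference falls from about 93% to about 81%. Declaring 50 the maximum gives up the freedom to go beyond it.

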## G2. Data Analysis

Provide a description of your plan for data analysis. State the types of comparisons you plan (e.g. comparison of means, comparison of proportions, regressions, analysis of variance). Which is the PRIMARY comparison/analysis? How will the analyses proposed relate to the primary purposes of your study?

The primary outcomes are time to granulation, successful granulation at 8 weeks, and number of failures (e.g. amputation, infection, rejection, re-application) within 8 weeks. Mixed models accommodate the longitudinal design; allow for testing differences between groups in patterns over time as well as at specific time points; are consistent with an intention to treat analysis (9), and are valid for data which are missing completely at random or at random (10). Number of failures as well as number of recurrence of ulcers over the 6 month follow-up will be modelled with a generalized linear model using an appropriate count outcome (Poisson, zero-inflated Poisson, negative binomial for overdispersion). Rate ratios comparing intervention arms will be estimated from this model. Appropriate mixed models (linear or generalized linear, for noncontinuous outcomes or logistic regression for binary data) will be used to test the intervention effect for each of the secondary outcomes (e.g. tissue biomechanics, mobility, patient centered outcomes, recurrence of ulcers, etc). A Kaplan-Meier survivorship analysis will be used for estimating time to event for none successful healing probability over time by treatment and the p-value will be calculated using the Log-rank (Mantel-Cox) test. Hazard ratios will be used to indicate the probability of closure at any given point in time for Derma-Cell v. Integra treatment. Univariate logistic regression analyses will be performed to delineate predictive factors of successful granulation at 8 weeks, successful wound healing at 12 weeks, and successful wound healing at 16 weeks. Results will be controlled for potential confounding variables including age, sex, BMI, HbA1c, neuropathy severity, vascular status, frailty, mobility status, and initial wound size. The p-values for weekly % wound area and % wound area reduction through 16 weeks will be calculated using t tests. All p-values, for both the categorical and continuous data, will be calculated using a two-sided alpha of 0.05.

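### The secondary outcome of healing speed after granulation exists only for wounds that granulated, so testing it between arms compares subsets selected by a primary outcome

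*Combined protocol and SAP*

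**What the plan says.** F1 (Design) sets the primary outcomes: "The primary outcomes are time to granulation, successful granulation at 8 weeks, and number of failures", the failures being counted within 8 weeks. Among the secondary outcomes it lists "weekly speed of wound healing after successful granulation and transition to standard wound therapy".

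G2 (Data Analysis) says that mixed models of a suitable type "will be used to test the intervention effect for each of the secondary outcomes". It describes such models in general as methods that "are consistent with an intention to treat analysis", and valid when data are missing at random. It names no analysis population for healing speed. It gives no rule for a wound that does not granulate, is re-grafted or is amputated.

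G2 also plans healing analyses with no stated granulation condition: "The p-values for weekly % wound area and % wound area reduction through 16 weeks will be calculated using t tests"; Kaplan-Meier curves with a log-rank test; and "Hazard ratios will be used to indicate the probability of closure at any given point in time for Derma-Cell v. Integra treatment". Section D names "weekly wound size change, time to heal, time to successful wound granulation" as wound outcomes, again without the condition.

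**The concern.** Randomisation makes the two arms comparable at matrix application. It does not make the granulated wounds of one arm comparable with the granulated wounds of the other. If one product brings 80% of wounds to granulation and the other 50%, the second group may hold a more favourable selection of wounds. Its average speed after granulation can then be higher although neither product affects speed.

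The clock is also a problem. It starts at a date that the product may change, so early and late granulators are measured over different parts of the 16 weeks.

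The result would be reported as an intervention effect, and a reader would take it for a randomised comparison. G1 (Sample Size) says that observed trends may lead to another RCT or a larger sample, so a spurious trend in a secondary outcome could have consequences.

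**Working it through.** **Inputs from the documents**
- Sample size: 17 per group (F1 and G1). F1 and G1 also give a total of 50, which is 25 per group if split equally.
- Test level: two-sided 0.05 (G2).
- Granulation rate per arm, and correlation between ease of granulation and later speed: not given. Both are assumed below and varied.

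**The plan's own figure.** The 17 per group rests on application time (3±2 versus 5±2 minutes, d = 1, power 80%). The two-sample t test gives 16.7, rounded up to 17, with power 80.7%. The figure reproduces, but it does not concern healing speed. The plan gives no figure for this endpoint.

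**Model for the selection.** Healing speed has the same normal distribution in both arms, so the product has no effect on it. A wound granulates when a normal latent tendency passes a threshold. Speed has correlation ρ with that tendency. For granulation probability p and z = Φ⁻¹(p), the mean speed of granulated wounds, in SD units, is ρ·φ(z)/p. Hence

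bias in favour of the lower-granulating arm = ρ·[φ(z_low)/p_low − φ(z_high)/p_high].

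Values of φ(z)/p: 0.798 at 50%, 0.644 at 60%, 0.497 at 70%, 0.350 at 80%, 0.195 at 90%.

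| Granulated, higher v. lower arm | Difference in φ(z)/p | ρ = 0.3 | ρ = 0.5 | ρ = 0.7 |
|---|---|---|---|---|
| 70% v. 50% | 0.301 | 0.09 SD | 0.15 SD | 0.21 SD |
| 80% v. 50% | 0.448 | 0.13 SD | 0.22 SD | 0.31 SD |
| 90% v. 60% | 0.449 | 0.13 SD | 0.22 SD | 0.31 SD |
| Equal rates | 0 | 0 | 0 | 0 |

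With ρ = 0 every entry is zero.

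**Patients left.** At 80% versus 50%, 17 per arm leaves 17 × 0.8 = 13.6 and 17 × 0.5 = 8.5. With 25 per arm it leaves 20 and 12.5.

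**Effect on the test.** Simulation with 4,000 trials per setting, no true difference in speed, and a t test on granulated wounds, for ρ = 0.3, 0.5 and 0.7:

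| Setting | Lower-granulating arm looks faster | False-positive rate |
|---|---|---|
| 80% v. 50%, 17 per arm | 62%, 72%, 79% | 0.07, 0.08, 0.12 |
| 80% v. 50%, 25 per arm | 64%, 75%, 84% | 0.07, 0.10, 0.15 |
| 90% v. 60%, 17 per arm | 63%, 72%, 81% | 0.06, 0.08, 0.14 |
| 90% v. 60%, 25 per arm | 65%, 76%, 85% | 0.06, 0.10, 0.17 |

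The same test on all randomised patients rejected in 0.044 to 0.056 of trials. That comparator is idealised, because it gives every wound a speed, including those that did not granulate.

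**Visit schedule (F2).** Granulation assessment is listed at weeks 5, 6, 7, 8 and 16. Wound assessment is listed at baseline and weeks 2, 4, 8, 10, 12, 14 and 16. Photographs are listed at every visit. The conditional outcome therefore starts at different weeks in different patients. A wound first recorded as granulated at week 16 has no scheduled follow-up in which its speed could be measured.

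**The case against.** A reader might infer that the plan compares healing only among granulated wounds. The documents do not support that. G2 tests weekly wound area and area reduction through 16 weeks and time to closure, and F1 lists healing at 12 and 16 weeks, none with a stated granulation condition. Much of the remedy is thus already planned, and the problem belongs to one endpoint.

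A reader might also infer that the comparison will favour the worse product. That needs two premises that the documents do not supply: unequal granulation, and faster healing in wounds that granulate easily. Section D assumes that wound outcomes are comparable between the products, and under this model equal rates give no selection bias.

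G2 adds covariate control: "Results will be controlled for potential confounding variables including age, sex, BMI, HbA1c, neuropathy severity, vascular status, frailty", with mobility status and initial wound size. Adjustment could lower the residual correlation. It removes the selection only so far as these nine variables explain both granulation and speed, and in the 80% versus 50% example at 17 per arm only about 22 patients remain to support it.

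The intention-to-treat and missing-at-random statements do not help here. The speed after granulation of a wound that never granulated is undefined rather than missing.

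Finally, the outcome is secondary, the study is labelled a pilot, and stage-specific speed is a legitimate description of a two-stage treatment. All of that stands. It argues for keeping the outcome as description, and does not justify a treatment test on it.

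**Conclusion.** The concern holds for the named endpoint. As defined, it conditions on a primary outcome and starts at a date that the product may change, so an intervention effect tested on it is not a randomised comparison. That conclusion follows from F1 and G2 and needs no assumption.

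The direction and size do rest on assumptions. The bias is about 0.1 to 0.3 SD in favour of the lower-granulating product for rates of 70–80% versus 50% and correlations of 0.3–0.7, and zero if the rates are equal or the correlation is zero. The effect of the varying start date was not quantified.

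The primary outcomes are not affected, nor on their stated terms are the other healing analyses, although G2 does not name their population either. The change is worth making because it is cheap and because, as written, the plan has two definitions of healing speed that may disagree and does not say which carries the treatment comparison.

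**What to change.** Changes to F1 and G2:
- Make the between-arm healing-speed comparison the wound-area change through week 16 already planned in G2, measured from matrix application, in all randomised patients by assigned arm. Use the mixed model that G2 already names in place of separate t tests, on the scheduled wound assessments (baseline and weeks 2, 4, 8, 10, 12, 14 and 16).
- Keep re-grafted wounds in their randomised arm. An amputated wound has no later area, so add a supporting analysis that counts it as not healed instead of treating it as missing at random.
- Report speed after granulation descriptively, without a treatment p-value, beside the number granulated per arm.

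The cost is a few sentences. No visit or measurement is added. The small downside is that speed from application mixes the granulation and closure phases, which is why the post-granulation figure is kept as description.
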